6.3.2.1.2. Derivation of a secondary definition of COVID-19

A secondary definition of COVID-19 is defined as any of the listed systemic symptom in Section 8.1.1 of the protocol AND with a positive RT-PCR test.

Date of the documented secondary definition of COVID-19 will be later date of:

- Date of the positive RT-PCR test (prompt by symptom)
- Date of eligible symptom for secondary definition of COVID-19, defined as the earliest date of first eligible symptom is reported

and the two dates should be within 14 days of each other.

The same censoring rule as summarized in Table 2 for the primary definition of COVID-19 will be used for the secondary definition of COVID-19 and corresponding sensitivity analyses with cases starting at different timepoint.

6.3.2.1.3. Derivation of serologically confirmed SARS-CoV-2 infection or COVID-19 regardless of symptomatology or severity

For the secondary efficacy endpoint: serologically confirmed SARS-CoV-2 infection or COVID-19 regardless of symptomatology or severity [COV-INF], any post-baseline positive RT-PCR results will be considered, including those from the scheduled NP swab tests at Day 29 visit prior to the 2nd injection of IP as well as the those prompted by symptom(s). In addition, seroconversion due to infection will also be considered.

The analysis population for COV-INF will be the Per-Protocol Set and the mITT Set that include participants with negative SARS-CoV-2 status at baseline. Seroconversion due to infection is defined for participants with negative SARS-CoV-2 status at baseline as becoming seropositive (positive bAb specific to SARS-CoV-2 NP) as measured by *Roche Elecsys* on study (at scheduled visits post baseline). A COVID-19 case or secondary definition of COVID-19 case will always be an INF case.

The date of documented infection regardless of symptom [COV-INF] will be the earlier of:

- Date of positive post-baseline RT-PCR result, or
- Date of seroconversion due to infection

In the primary approach, documented infection is counted starting 14 days after the 2nd dose, which requires a positive RT-PCR result starting 14 days after the 2nd IP dose, or seroconversion at Day 57 visit or later.

Derivation of this secondary efficacy endpoint is summarized in [Table 3](#).

Table 3: Derivation of Secondary efficacy endpoint: Serologically confirmed SARS-CoV-2 infection or COVID-19 regardless of symptomatology or severity – mITT Set or Per-Protocol Set

Baseline SARS-CoV-2 Status	Post-baseline assessments		Secondary endpoint: serologically confirmed SARS-CoV-2 infection or COVID-19 regardless of symptomatology or severity
	PCR test post baseline	bAb levels against SARS-CoV-2 Nucleocapsid	
Negative at Baseline	positive (either at symptom-prompt NP swab test [Illness visit], or at scheduled NP swab test)		Case
Negative at Baseline		Seroconversion (positive on study at scheduled visits) as measured by Roche Elecsys	Case

6.3.2.1.4. Derivation of asymptomatic SARS-CoV-2 infection

Asymptomatic SARS-CoV-2 infection will be analyzed using the Per-Protocol Set and mITT Set. Asymptomatic infection is identified by absence of symptoms and infections as detected by RT-PCR or seroconversion. Specifically:

- Absent of symptoms (no COVID-19 symptom for either primary efficacy endpoint of COVID-19, or secondary definition of COVID-19),
- AND at least one from below:
 - seroconversion (bAb specific to SARS-CoV-2 nucleocapsid) at scheduled visits (months 1, 2, 7, 13 and 25 if applicable in Part A, Participant Decision Visit and etc. in Part B), when blood samples for immunogenicity are collected, or
 - by RT-PCR at scheduled visits such as pre-dose 2 at Day 29 in Part A, both RT-PCR test and bAb against SARS-CoV-2 nucleocapsid will be considered.

The date of documented asymptomatic infection is the earlier date of seroconversion due to infection, or positive RT-PCR at scheduled visits, with absence of symptoms.

Participants who had a symptomatic infection (COVID-19 or secondary definition of COVID-19) prior to an asymptomatic infection will be censored at the time of symptomatic infection for the analysis of asymptomatic infection. In the primary approach, documented asymptomatic infection is counted starting 14 days after the 2nd IP dose, which requires seroconversion at months 2 (Day 57 visit) or later.

6.3.2.2. Analysis of the secondary efficacy endpoints

Similar analysis methods as for the primary efficacy endpoint will be applied to the following secondary efficacy endpoints based on the PP set, unless otherwise specified:

- VE to prevent severe COVID-19
- VE to prevent serologically confirmed SARS-CoV-2 infection or COVID-19 regardless of symptomatology or severity.

- VE to prevent COVID-19 using a secondary definition of symptoms
- VE to prevent death caused by COVID-19

For each of the above secondary objectives, the following analyses will be performed:

- Primary analysis: VE will be estimated with $1 - HR$ (mRNA-1273 vs. placebo) using a Cox PH model based on the PP Set as described for the primary efficacy endpoint. Kaplan-Meier curves of time to event will be presented for each treatment group.

Cases will be counted starting 14 days after the second injection of IP.

- Analysis using the same model based on the mITT Set as described for the primary efficacy endpoint. Kaplan-Meier curves of time to event will be presented for each treatment group.
- Sensitivity analyses with cases counted starting immediately after the second injection of IP (onset date \geq date of dose 2, considering positive RT-PCR at Day 29), starting 14 days (\geq 14 days) after the first injection of IP, and immediately after randomization respectively.
- VE and 95% CI based on the incidence will be estimated with $1 - \text{ratio of incidence rates}$ using the exact method conditional upon the total number of cases.

For the secondary efficacy objective: VE to prevent asymptomatic SARS-CoV-2 infection

As diseased cases (COVID-19 or secondary definition of COVID-19) are competing events for asymptomatic SARS-CoV-2 infections, competing risk method will be used to estimate the vaccine efficacy of mRNA-1273, specifically, Fine and Gray's (FG) sub-distribution hazard model will be used. Competing risk method will also be used to estimate the cumulative incidence function and the cumulative incidence of asymptomatic SARS-CoV-2 infections will be plotted.

In the primary approach with cases of asymptomatic SARS-CoV-2 infection counted starting 14 days after the second injection, only seroconversion at Day 57 or later will be considered.

As serum samples were taken at scheduled visits (e.g. Day 29[month 1], Day 57[month 2]), sensitivity analyses with cases counted starting after 2nd dose, 14 days after first dose, after first dose and after randomization are the same. Only one set of sensitivity analysis with cases counted starting from randomization will be provided. In this sensitivity analysis, asymptomatic cases detected by positive RT-PCR result at scheduled pre-dose 2 visit (Day 29), or seroconversion at timepoints with scheduled visits will be considered. Sensitivity analysis using the mITT Set with cases counted starting from 14 days after the second injection, and from randomization will also be performed.

Stratified Cox PH model may also be used.

For the secondary efficacy objective: VE to prevent COVID-19 after the first injection of IP

This endpoint will be analyzed as a sensitivity analysis of the primary efficacy endpoint with cases counted starting 14 days (≥ 14 days) after the first injection of IP as described in [Section 6.3.1](#).

For the secondary efficacy objective: VE to prevent COVID-19 disease regardless of prior SARS-CoV-2 infection

This endpoint will be analyzed using the FAS. The same methods described above for the primary efficacy endpoint will be applied with cases counted starting 14 days after the second injection of IP.

Sensitivity analyses with cases counted starting immediately after the second injection, 14 days after the first injection, and after randomization will also be performed. In sensitivity analysis with cases counted starting after the second

injection, subjects who received only the first injection and is a case will be censored at the time of COVID-19.

The VE will also be estimated with 1- ratio of incidence rates with the 95% CI using the exact method conditional upon the total number of cases adjusting for person-time.

In addition, an exploratory analysis with the same Cox model will be carried out in the subgroup of FAS whose baseline SARS-CoV-2 status is positive with cases counted starting from randomization to assess the VE in those with positive baseline SARS-CoV-2 status, at baseline, if sample size permits. Such analysis in the subgroup of FAS whose baseline SARS-CoV-2 status is negative with cases counted starting from randomization is the same as the sensitivity analysis of COVID-19 starting from randomization in mITT.

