4. Participants with symptoms of COVID-19 will be asked to return within 72 hours or as soon as possible to the study site for an unscheduled visit, to include an NP swab sample (for RT-PCR testing) and other clinical evaluations. If a study site visit is not possible, a home visit may be arranged to collect the NP swab sample and conduct clinical evaluations. If a home visit is not possible, the participant will be asked to submit a saliva sample to the study site by a Sponsor-approved method. At this visit, an NP swab and blood sample will be collected to evaluate for the presence of SARS-CoV-2 infection. An additional NP swab sample will be collected to test for the presence of other respiratory pathogens. Additionally, clinical information will be carefully collected to evaluate the severity of the clinical case. It is important to note that some of the symptoms of COVID-19 overlap with solicited systemic ARs that are expected after vaccination with mRNA-1273 (eg, myalgia, headache, fever, and chills). During the first 7 days after vaccination, when these solicited ARs are common, investigators should use their clinical judgement to decide if an NP swab should be collected. The collection of an NP swab prior to the Day 1 and Day 29 vaccination can help ensure that cases of COVID-19 are not overlooked. Any study participant reporting respiratory symptoms during the 7-day period after vaccination should be evaluated for COVID-19.
5. Sample must be collected prior to dosing on days of injection (Day 1 and Day 29).
6. The participant will record entries in the eDiary approximately 30 minutes after dosing while at the study site, with instruction provided by study staff. Study participants will continue to record in the eDiary each day after they leave the study site, preferably in the evening, on the day of dosing and for 6 days following. Any solicited AR that is ongoing beyond Day 7 will be reported until resolution. Adverse reactions recorded in eDiaries beyond Day 7 should be reviewed either via phone call or at the following study visit. Participants will be given thermometers to record their temperatures and rulers to measure any injection site reactions.

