- b) study day on or after the date of the first injection will be calculated as: date of assessment/event – date of the first injection + 1;

Study day relative to the most recent injection will be calculated as below:

- a) study day prior to the first injection will be calculated as: date of assessment/event – date of the first injection;
- b) study day on or after the date of the first injection but before the second injection (if applicable) will be calculated as: date of assessment/event – date of the first injection + 1;

- c) study day on or after the date of the second injection will be calculated as: date of assessment/event – date of the second injection + 1; if study day is on the same day as the second injection, date and time will be compared with the second injection date and time. If it is prior to the second injection, then study day is calculated as b); If it is after the second injection or the time is missing or not available then study day is calculated as: date of assessment/event – date of the second injection + 1.

Unscheduled visits: Unscheduled visit measurements will be included in analysis as follows:

- In scheduled visit windows per specified visit windowing rules.
- In the derivation of baseline measurements.
- In the derivation of maximum/minimum values after 1st dose and maximum/minimum change from baseline values for safety analyses.
- In individual subject data listings as appropriate.

Visit windowing rules: The analysis visit windows for protocol-defined visits are provided in [Appendix B](#).

Incomplete/missing data:

- Imputation rules for missing dates of prior/concomitant medications, non-study vaccinations and procedures are provided in [Appendix C](#).
- Imputation rules for missing AE dates are provided in [Appendix D](#).
- If the laboratory results are reported as below the LLOQ (e.g. < 0.1), the numeric values will be substituted by $0.5 \times \text{LLOQ}$ in the summary when treating the results as continuous variables. If the laboratory results are reported as greater than the ULOQ (e.g. > 3000), the numeric values will be substituted by ULOQ in the summary statistics for continuous variable.
- Other incomplete/missing data will not be imputed, unless specified otherwise.

Treatment groups

The following treatment groups will be used for summary purposes in Part A:

- mRNA-1273
- Placebo

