 - Respiratory symptom: earliest date of an eligible respiratory symptom is reported
 - Systemic symptoms: earliest date of the 2nd eligible systemic symptom is reported

The time to the first occurrence of COVID-19 will be calculated as:

Time to the 1st occurrence of COVID-19 = Date of documented COVID-19 – Date of randomization +1.

In the primary analysis approach for the primary efficacy endpoint, cases will be counted starting 14 days after the 2nd injection, i.e. date of documented COVID-19 – Date of the 2nd injection \geq 14 (starting 14 days after the 2nd injection).

In the primary analysis approach for the primary efficacy endpoint, the first occurrence of COVID-19 starting 14 days after the 2nd injection will be considered event. In the various sensitivity analyses planned to examine the onset of COVID-19, the censoring rules of cases are outlined in Table 2 below.

In this study, during the blinded phase, there is a scheduled NP swab test at the Day 29 visit prior to the 2nd injection of IP; and blood samples are collected with bAb against SARS-CoV-2 nucleocapsid (NP) tested at months 1, 2, 7, 13 and 25. At IA1 and the Primary Analysis of efficacy, RT-PCR results at scheduled pre-dose 2 (Day 29) and bAb against SARS-CoV-2 nucleocapsid at Day 29 were not considered in the derivation of COVID-19.

At the final blinded efficacy analysis, subjects with early infection, as detected by positive RT-PCR at scheduled pre-dose 2 visit (Day 29), or positive bAb against SARS-CoV-2 NP in blood samples at the scheduled visits, are censored at the time of early infection. If a participant had eligible symptom(s) within 14 days of positive RT-PCR at scheduled pre-dose 2 visit, the participant is considered to be a case for COVID-19.

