6.3.1.3. Sensitivity Analyses with COVID-19 Cases Counted Starting at Various Timepoints

Sensitivity analyses will be performed with COVID-19 cases counted starting at various timepoints as below using the PP Set. The censoring rules for analyses of the primary endpoint are summarized in Table 2.

- immediately after the second injection of IP
- 14 days after the first injection of IP (also as primary analysis approach for the secondary efficacy objective: To evaluate the efficacy of mRNA-1273 to prevent COVID-19 after the first dose of IP.)
- immediately after the first injection of IP
- immediately after randomization

If <10% of the COVID-19 cases received the first injection after the day the subject was randomized, sensitivity analysis with COVID-19 cases counted starting after the first injection of IP may not be performed separately, as it would be very similar to the sensitivity analysis with COVID-19 cases counted starting from randomization.

Table 2: Censoring Rules for COVID-19

Situation	Primary Efficacy Approach (cases ≥ 14 days after Dose 2)	Sensitivity Analyses			
		Cases starting after Dose 2	Cases ≥ 14 days after Dose 1	Cases starting after Dose 1*	Cases starting after randomization
Early case from randomization up to first injection	Censored at date of case	Censored at date of case	Censored at date of case	Censored at date of case	Event
Early case from Dose 1 up to ($<$) 14 days after Dose 1	Censored at date of case	Censored at date of case	Censored at date of case	Event	Event
Early case from ≥ 14 days after Dose 1 up to ($<$) Dose 2	Censored at date of case	Censored at date of case	Event	Event	Event
Early case from Dose 2 up to ($<$) 14 days after Dose 2	Censored at date of case	Event	Event	Event	Event
Case ≥ 14 days after Dose 2	Event	Event	Event	Event	Event
Early discontinuation or death without documentation of COVID-19	Censored at date of discontinuation/death				

Situation	Primary Efficacy Approach (cases \geq14 days after Dose 2)	Sensitivity Analyses			
		Cases starting after Dose 2	Cases \geq14 days after Dose 1	Cases starting after Dose 1*	Cases starting after randomization
Early infection as detected by: positive RT-PCR at scheduled visit (pre-dose 2), or, positive bAb against SARS-CoV-2 NP in blood samples at the scheduled visits	Censored at date of early infection				

* To be performed if there are \geq 10% of total cases with Dose 1 date > randomization date

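### For infection (COV-INF), the sensitivity analysis meant to start after Dose 2 counts positive Day 29 samples that were taken before Dose 2

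*SAP*

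**What the plan says.** - **The rule.** SAP Part A 6.3.2.2 lists sensitivity analyses for severe COVID-19, COV-INF, the secondary definition of COVID-19 and COVID-19 death. The one that starts at the second injection takes onset on or after the "date of dose 2, considering positive RT-PCR at Day 29". Protocol Table 9 and section 9.5.1.2 describe it simply as cases starting after the second dose.
- **What a COV-INF event is.** SAP Part A 6.3.2.1.3 accepts any positive post-baseline RT-PCR, "including those from the scheduled NP swab tests at Day 29 visit prior to the 2nd injection of IP". SAP Table 3 repeats that a positive scheduled swab is a case. Seroconversion at a scheduled visit also qualifies. The event date is the earlier of the positive PCR and the seroconversion.
- **When the Day 29 samples are taken.** SAP Part A 6.3.1.1 says "there is a scheduled NP swab test at the Day 29 visit prior to the 2nd injection of IP". Protocol Table 16, footnote 5, is attached to both the swab row and the blood row: "Sample must be collected prior to dosing on days of injection (Day 1 and Day 29". SAP 6.3.1.1 lists month 1 among the times at which nucleocapsid antibody is tested.
- **Primary COV-INF approach.** It needs a positive PCR at least 14 days after Dose 2, or seroconversion at Day 57 or later.
- **Table 2.** "The censoring rules for analyses of the primary endpoint are summarized in Table 2". Its row for early infection, including "positive RT-PCR at scheduled visit (pre-dose 2", has the single entry "Censored at date of early infection". Section 6.3.2.1.2 extends Table 2 by name to the secondary definition of COVID-19. No section extends it by name to COV-INF.

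**The concern.** The label and the rule disagree. The analysis is presented as starting after Dose 2, but for COV-INF the rule admits infections found in samples that must be collected before Dose 2 is given. Those infections were acquired after one dose.

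The purpose of varying the start point is to show how efficacy behaves from each point onward. If one-dose infections enter the post-Dose 2 window, a gap between this result and the primary approach cannot be read as protection building up after Dose 2. COV-INF is second in the fixed testing sequence of SAP Part A 6.5, so its supporting analyses are likely to be read closely, although nothing in 6.5 ties the formal test to this one.

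**Working it through.** The SAP states no figure for this analysis, so there is none to reproduce. The check follows the rule through, then looks at direction and size.

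**Step 1: same-day swab and Dose 2.** Let both fall on date d, swab first. The swab is positive, so the COV-INF date is d. The rule asks whether d is on or after d. It is, so the participant is a post-Dose 2 event. Day 29 blood is drawn before the same injection, so a Day 29 seroconversion dated d passes as well.

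**Step 2: Dose 2 on a later date.** If Dose 2 is on d + k with k of at least 1, the swab date d is before it and the date rule excludes the swab. The added reference to the Day 29 PCR then conflicts with the date rule beside it. The line needs repair in either case.

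**Step 3: the other endpoints.** For COVID-19, 6.3.1.1 makes a positive Day 29 PCR a case only if eligible symptoms fall within 14 days of it, dated at the later of the two. Table 2 covers the secondary definition through 6.3.2.1.2, and severe COVID-19 requires a confirmed COVID-19 case. These endpoints therefore have a reading of 6.3.2.2 that fits Table 2. Asymptomatic infection is handled separately, with only a from-randomization sensitivity analysis. The problem is specific to COV-INF.

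**Step 4: direction and size.** Let q be the share of placebo-arm events in this analysis that come from pre-dose Day 29 samples, VE1 the one-dose efficacy against infection and VE2 the efficacy after Dose 2. Assume equal person-time. Scale placebo events to 1. Vaccine events are q(1 − VE1) + (1 − q)(1 − VE2), so

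VE estimated = q × VE1 + (1 − q) × VE2.

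For example, with q = 0.10, VE1 = 0.30 and VE2 = 0.60: 0.03 + 0.54 = 57.0%.

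| VE2 | VE1 | q = 5% | q = 10% | q = 20% | q = 30% |
|---|---|---|---|---|---|
| 60% | 0% | 57.0 | 54.0 | 48.0 | 42.0 |
| 60% | 30% | 58.5 | 57.0 | 54.0 | 51.0 |
| 60% | 50% | 59.5 | 59.0 | 58.0 | 57.0 |
| 93% | 0% | 88.35 | 83.7 | 74.4 | 65.1 |
| 93% | 50% | 90.85 | 88.7 | 84.4 | 80.1 |

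The 60% is the design value for COV-INF in SAP Part A 4.3. The 93% is the efficacy against COVID-19, not infection, reported in protocol 2.2.2, and is used only as a high value. VE1 and q are assumptions throughout. If VE1 = VE2 nothing moves. If the Day 29 positives are censored, q is 0 and the formula returns VE2.

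**The case against.** The strongest reply has four parts.

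- **The wording is not explicit.** The SAP says that the Day 29 PCR is considered, and does not define the term. This is true, but elsewhere the SAP uses the word for inclusion: in 6.3.2.1.3 for PCR results that count, and in 6.3.2.2 for asymptomatic cases from the pre-Dose 2 swab. Counting is the natural reading, and for COV-INF the date rule alone already admits a same-day positive.
- **Table 2 is not contradicted.** A reader might infer a direct clash, because Table 2 censors this same swab. The documents do not support that for COV-INF. Table 2 is written for COVID-19 and extended by name only to the secondary definition. Its early-infection row would also censor the scheduled PCR and serology positives that are themselves COV-INF events. This objection stands, and no contradiction with Table 2 is claimed for infection.
- **Section 6.1 is not a case-counting rule.** It says of a same-day assessment, "If it is prior to the second injection, then study day is calculated as b", which places it in the Dose 1 period. That is a study-day convention. It offers a method for the fix but does not show a second conflict.
- **Little depends on it.** Only one sensitivity analysis is affected, and where one-dose efficacy is lower the error understates VE. The SAP for Parts B and C describes the Part A analyses as completed. All of this stands and limits the importance of the point, but the rule still misassigns events.

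**Conclusion.** The point holds for COV-INF. As written, the after-Dose 2 sensitivity analysis counts infections found in samples taken before Dose 2. The conclusion rests on same-day sampling and dosing and on the SAP's own dating of COV-INF events. The pull toward one-dose efficacy follows if one-dose efficacy against infection is below two-dose efficacy.

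The size is not determinable. A reader might build one from an assumed constant attack rate, 7 to 14 days of swab positivity, 60 to 180 days of follow-up and one-dose VE of 30% to 60%. A true 90% would then appear as 1 − (60 × 0.1 + 14 × 0.7)/74 = 78.6% at one end and 1 − (180 × 0.1 + 7 × 0.4)/187 = 88.9% at the other. The documents support none of those inputs as applied to this analysis. The 60-day case resembles the November 2020 analysis, when SAP Part A 6.5 says infection data were not available. Infections already documented before Day 29 carry an earlier date, and participants without Dose 2 within 21 to 42 days are outside the PP Set, so fewer infections would enter through the Day 29 swab than that model assumes.

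It would also be wrong to infer that the main infection result is in doubt. The primary COV-INF approach does not use this rule. This is a minor error with a specific correction.

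**What to change.** In SAP Part A 6.3.2.2, separate the rule by endpoint.

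- **COV-INF:** start the after-Dose 2 window after the Dose 2 injection, by date and time. In this analysis only, censor a positive pre-dose Day 29 RT-PCR or nucleocapsid serology as an infection before the window. Keep it as an event in the analyses from randomization and from 14 days after Dose 1. Section 6.1 treats a same-day assessment with missing time as after the injection, so scheduled Day 29 samples without a time should be classed as pre-dose, in line with the protocol's collection rule.
- **COVID-19 definitions:** state that Table 2 and the rule on symptoms within 14 days in 6.3.1.1 govern a positive Day 29 PCR.
- **Reporting:** give the number of positive Day 29 PCR and serology results by arm, so that the effect on the estimate can be seen.

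The cost is a short wording change and a re-run of one sensitivity analysis. Because the Part A analyses are described as completed, with a study report dated 03 August 2021, the re-run should be labelled post hoc.
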